### 1) Have any data been collected for this study already?

No, no data have been collected for this study yet.

### 2) What's the main question being asked or hypothesis being tested in this study?

Whether the race and gender of a simulated doctor causes participants in an analogue patient experiment to give lower satisfaction ratings and report less confidence in their diagnosis. The main (null) hypothesis being tested is that there are no differences across four treatment arms that randomize the race and gender of a putative doctor.

### 3) Describe the key dependent variable(s) specifying how they will be measured.

Primary outcome measures:

Aspredicted

- How confident are you that this doctor made the correct diagnosis? [not at all confident (1) to completely confident (5)]
- How confident are you that this doctor recommended the correct treatment plan? [not at all confident (1) to completely confident (5)]
- Which diagnosis do you think is more likely to be correct? [the doctor's diagnosis (1); online symptom checker (2)]

• Would you ask the doctor to perform additional diagnostic tests? (Such as the CT scan recommended by the Symptom Checker). [definitely not (1); probably not (2); might or might not (3); probably (4); definitely (5)]

2) Satisfaction.

• What number would you use to rate your care during this emergency room visit? [0 (worse possible care) to 10 (best possible care)]

• Would you recommend this doctor to your friends and family? [definitely not (1); probably not (2); might or might not (3); probably (4); definitely (5)]

Secondary outcome measures:

1) Warmth and Competence of Doctor (6-item warmth-competence scale)

2) Willingness to file a complaint. Willing to sue if a diagnostic mistake was made [both: definitely not (1); probably not (2); might or might not (3); probably (4); definitely (5)]

### 4) How many and which conditions will participants be assigned to?

This is a 2x2 experimental design. Subjects will be randomly assigned to one of four possible conditions: Black Female, Black Male, White Female, White Male. Within each condition, subjects are randomly assigned 1 of 10 possible putative doctors. We have a total of 40 putative doctors, 10 for each condition. For example, 10 Black Female doctors, etc. These are, in fact, actors selected from the Chicago Face Database. Given that the vast majority of Emergency Physicians in the United States are white men, the White Males condition serves as the "control".

### 5) Specify exactly which analyses you will conduct to examine the main question/hypothesis.

For all enumerated outcome variables, we will use a linear regression of the outcome on treatment assignment (with White Male as the omitted category), with robust standard errors. In addition to the basic "difference in means" estimator, we will also conduct regression analyses with covariate adjustment. In addition to standard demographic covariates, we also include a measure of trust in doctors, self-assessed health, insurance coverage status, recent emergency department visit experience, the gender and race of the respondent's primary care doctor (if applicable), and whether subjects have unpaid medical bills. Previous results indicated that trust in doctors is the most prognostic covariate.

We also plan to conduct the following sub-group analyses to estimate conditional average treatment effects:

1) By sex (male or female).

2) Age (individuals born before 1965 versus those born in 1965 or after)

3) Race (black or white)

4) Prejudice. We have a 4-item measure of racial prejudice (Stereotype Endorsement) and an 5-item measure of gender prejudice (from the Ambivalent Sexism Inventory)

We also plan to conduct exploratory analyses of treatment effect heterogeneity using Bayesian Additive Regression Trees (BART).

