## 7) How many observations will be collected or what will determine sample size? No need to justify decision, but be precise about exactly how the number will be determined.

We will collect 1600 observations in total for a target of 0.80 power to estimate a Minimum Detectable Effect (MDE) of 0.10 standard units for the

Aspredicted Pre-Registration made easy

primary outcome variables. The MDE calculations are based on the results from the previous experiment.

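### The one named age sub-group analysis is a single cut at birth year 1965; a continuous birth-year-by-arm term beside it would recover the information about an age gradient that the cut gives up

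*SAP*

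**What the plan says.** The SAP holds two registrations: a replication, and the earlier MTurk study that it repeats. The relevant statements in the replication are these.

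- Question 5 introduces the sub-groups with "We also plan to conduct the following sub-group analyses to estimate conditional average treatment effects". The age item is "Age (individuals born before 1965 versus those born in 1965 or after". The MTurk registration has the same cut under its own question 5.
- Neither registration gives a reason for 1965, an expected number on either side of the cut, a second cut, or an interaction of arm with age.
- The main model in question 5 is a "linear regression of the outcome on treatment assignment (with White Male as the omitted category), with robust standard errors". It is also run with covariate adjustment, described as "In addition to standard demographic covariates, we also include a measure of trust in doctors" followed by further items. Age is not named there and its form is not given.
- The same answer adds "We also plan to conduct exploratory analyses of treatment effect heterogeneity using Bayesian Additive Regression Trees (BART"). The moderators to be supplied to BART are not listed.
- Question 4 has four arms: "Subjects will be randomly assigned to one of four possible conditions: Black Female, Black Male, White Female, White Male". Question 7 sets the size: "We will collect 1600 observations in total for a target of 0.80 power to estimate a Minimum Detectable Effect (MDE) of 0.10 standard units".

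**The concern.** A rule based on birth year implies that birth year, or age, is collected. The named analysis then reduces it to two groups. Comparing two group averages is a legitimate summary, but it ignores how age varies within each group. If bias rises or falls steadily with respondent age, that within-group variation carries much of the evidence.

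At stake is how a null age result would be read. If the two birth-year groups show similar effects, a reader may take it that age does not matter, although the comparison could have missed a gradient that a continuous term would have detected. No primary hypothesis or estimate depends on this.

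**Working it through.** **The plan's own figure.** The SAP gives no power figure for the age sub-group. Its only figure is the overall detectable effect of 0.10 SD at N = 1600 and 0.80 power. With 400 per arm and two-sided alpha 0.05 (both assumed, neither stated), the multiplier is 1.960 + 0.842 = 2.802, and the unadjusted values are:

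- one arm against White Male: 2.802 × sqrt(2/400) = 0.198 SD;
- a race or gender main effect, 800 against 800: 2.802 × sqrt(2/800) = 0.140 SD.

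The 0.10 is therefore not reproduced without covariate adjustment. That is a separate matter, and the comparison below does not rest on it.

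**Inputs for the age comparison.** From the SAP: N = 1600, four arms, White Male as reference, one cut at 1965. Assumed: equal allocation, two-sided 0.05, outcome SD of 1, the share *p* born before 1965, and the shape of the age distribution.

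**Step 1, the linear term.** For one arm against White Male, with age in SD units, the slope has SE = sqrt(2/400) = 0.0707. The slope detectable with 0.80 power is 2.802 × 0.0707 = 0.20 SD of outcome per SD of age. For a main effect it is 2.802 × sqrt(4/1600) = 0.14.

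**Step 2, information kept by the cut.** For a truly linear gradient this is r², the squared correlation between age and the older/younger indicator:

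- normal age: r² = φ(z)² / [p(1−p)], where z is the cut-point. At p = 0.50: 0.3989²/0.25 = 0.64. At p = 0.10: 0.1755²/0.09 = 0.34;
- uniform age: r² = 3p(1−p). At p = 0.50: 0.75. At p = 0.10: 0.27;
- right-skewed age (gamma, shape 2): r² by simulation with 1,000,000 draws, 0.55 and 0.53.

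**Step 3, power with the cut.** Where the linear term has 0.80 power, the cut has power Φ(2.802 × r − 1.960). For normal age at p = 0.10: Φ(2.802 × 0.585 − 1.960) = Φ(−0.32) = 0.37.

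| Share born before 1965 (assumed) | Information kept: normal / uniform / skewed | Power with the cut: normal / uniform / skewed |
|---|---|---|
| 10% | 0.34 / 0.27 / 0.53 | 0.37 / 0.31 / 0.53 |
| 20% | 0.49 / 0.48 / 0.63 | 0.50 / 0.49 / 0.60 |
| 30% | 0.58 / 0.63 / 0.64 | 0.57 / 0.60 / 0.61 |
| 50% | 0.64 / 0.75 / 0.55 | 0.61 / 0.68 / 0.55 |

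The outcome variance and N cancel from r², so covariate adjustment does not change the relative loss. It depends only on the older share and the shape of the age distribution.

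**Step 4, what the cut does not explain.** For a slope of 0.10 SD per SD of age, the linear term itself has power Φ(0.10/0.0707 − 1.960) = Φ(−0.55) = 0.29. For gradients of that size the limit is mainly the sample size.

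**The case against.** The other side has a good case on several points.

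- **Age is not examined only through the cut.** BART needs no pre-set cut and is planned in the same answer. This stands. However, BART is exploratory and its moderators are not listed, so the cut remains the only named, pre-specified age analysis.
- **The stated aim is to estimate effects in sub-groups, not to test a gradient.** This also stands. Two group averages do not assume that the effect jumps at 1965. The loss matters only if the result is used to say whether bias varies with age, which is the natural use of an age sub-group.
- **The cut has merits.** It is fixed in advance and identical in both registrations, which limits data-driven choice and allows comparison with the first study. It would also suit a true generational step better than a line. This argues for keeping it, not against adding a term.

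A reader might infer more than the documents support:

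- *That the older group will be very small.* The SAP gives no age distribution, quota or expected share, and the replication's recruitment source is not stated. The warning about few Black respondents is in the MTurk registration, concerns race, and is absent from the replication. Excluding people with past cancer or abdominal surgery (question 6) may thin the older group, but by an amount that the SAP does not allow one to estimate.
- *That the cut discards most of the age information.* In the table this is so at 10% older under normal or uniform age, and only just at 20%. It is not so at 30% or 50%, or at any tabulated share under skewed age.
- *That a gradient will usually be missed.* Power with the cut is at or above one half in most cells, and the answer depends on a gradient size that nobody knows.

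**Conclusion.** The point holds as a modest loss of efficiency in a secondary analysis. For a roughly linear gradient, the 1965 cut keeps about 55-75% of the information at an even split and about 27-53% at 10% older. Power falls from 0.80 to about 0.55-0.68 and 0.31-0.53 respectively. Under none of the age distributions and shares tried did the cut match the linear term.

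The size rests on an assumed older share, three assumed age shapes and a linear gradient. If the true pattern is a step near 1965, the cut would fit it better than the line.

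**What to change.** Leave the 1965 split as registered. Beside it, in question 5 of the replication, add:

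- a full-sample model with the interaction of arm and centred, continuous birth year, named as the test of an age gradient, with a statement of whether the arm terms are tested jointly or each against White Male;
- a restricted cubic spline version, as a check on shape only;
- one line saying whether age enters BART uncut, and the expected share born before 1965 if it is known.

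The cost is a few sentences and one extra secondary test. No new data are needed if birth year or age is recorded as such, which the cut implies. The linear term is less sensitive to a true generational step, but the retained split covers that case. The primary analysis and the sample size stay as they are.

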### 6) Describe exactly how outliers will be defined and handled, and your precise rule(s) for excluding observations.

We exclude respondents who are not in the United States. The following exclusion criteria are also applied: 1) subjects who are currently pregnant are ineligible; 2) subjects who have had cancer or currently have cancer are ineligible; 3) subjects who have had abdominal surgery are ineligible.

## 7) How many observations will be collected or what will determine sample size? No need to justify decision, but be precise about exactly how the number will be determined.

We will collect 1600 observations in total for a target of 0.80 power to estimate a Minimum Detectable Effect (MDE) of 0.10 standard units for the

Aspredicted Pre-Registration made easy

primary outcome variables. The MDE calculations are based on the results from the previous experiment.

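### 1600 respondents in four arms do not give 0.80 power for 0.10 SD: each contrast with White Male has an MDE of about 0.20 SD and about 29% power at 0.10

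*SAP*

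**What the plan says.** The SAP file holds two pre-registrations: one for the replication, placed first, and one for the earlier MTurk study. The point concerns the replication.

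- **Question 7 (sample size):** "We will collect 1600 observations in total for a target of 0.80 power to estimate a Minimum Detectable Effect (MDE) of 0.10 standard units". This claim refers to the primary outcomes. On the source of the figure the section adds: "The MDE calculations are based on the results from the previous experiment".
- **Question 4 (conditions):** "Subjects will be randomly assigned to one of four possible conditions: Black Female, Black Male, White Female, White Male". White Male is named as the control.
- **Question 5 (analyses):** a "linear regression of the outcome on treatment assignment (with White Male as the omitted category), with robust standard errors". The unadjusted comparison of means is the basic estimator, and covariate-adjusted regressions are run in addition.

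The allocation ratio, alpha, sidedness, the contrast being powered and any assumed R-squared are not given. The MTurk pre-registration also gives 1600 and 0.80 power but no effect size, so the discrepancy is specific to the replication.

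**The concern.** The 1600 is a total over four arms, but the regression compares single arms with White Male, so each estimate rests on about half the sample. An effect of 0.10 SD is small for a comparison of 400 with 400.

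The stated MDE is the plan's only statement of sensitivity, and it governs how a null result is read. A reader who trusts it would take a true 0.10 SD difference by doctor race or gender as detectable four times in five. If the figure is wrong by a factor of two, a null result says much less about small bias than the plan implies.

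**Working it through.** **Inputs from the SAP (replication):** total N = 1600, target power 0.80 and MDE 0.10 (question 7); four arms (question 4); White Male as reference (question 5).

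**Assumptions, because the plan is silent:** equal arms, so 1600/4 = 400 each; alpha 0.05 two-sided; outcome SD = 1, so that 0.10 standard units is a mean difference of 0.10 SD; no loss of respondents, since exclusions are applied before data collection.

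**Formulas**

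- SE = sqrt((1 − R²)(1/n1 + 1/n2))
- MDE at 0.80 power = (1.960 + 0.842) × SE = 2.802 × SE
- Power at 0.10 = Φ(0.10/SE − 1.960)

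**Planned contrast, 400 v 400, R² = 0**

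- SE = sqrt(2/400) = 0.0707
- MDE = 2.802 × 0.0707 = 0.198 SD
- Power at 0.10 = Φ(1.414 − 1.960) = Φ(−0.546) = 0.293. A noncentral t calculation on 1596 df also gives 0.293.
- n per arm for 0.80 power at 0.10 = 2 × 2.802²/0.10² ≈ 1570, or 4 × 1570 = 6280 in total
- 95% CI half-width = 1.960 × 0.0707 = 0.139 SD

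The stated combination of 1600, 0.80 and 0.10 is therefore not reproduced.

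**Other mean-difference readings, also at 1600 in total**

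| Reading | MDE (SD) | Power at 0.10 SD |
|---|---|---|
| 400 v 400, two-sided 5% | 0.198 | 0.293 |
| 400 v 400, one-sided 5% | 0.176 | 0.409 |
| Race or gender main effect, 800 v 800 (SE 0.05), two-sided | 0.140 | 0.516 |
| Same, one-sided 5% | 0.124 | 0.639 |
| White Male v other three pooled, 400 v 1200, two-sided | 0.162 | 0.410 |
| 400 v 400, Bonferroni over three contrasts | 0.229 | 0.164 |

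The pooled main effect would need 2 × 1570 = 3140 in total. A 3-df omnibus F test has power 0.274 if one arm, or three arms, are shifted by 0.10 SD, and 0.358 if two are.

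**Covariate adjustment (two-sided 5%)**

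| R² | 400 v 400: MDE, power at 0.10 | 800 v 800: MDE, power at 0.10 |
|---|---|---|
| 0.1 | 0.188, 0.319 | 0.133, 0.559 |
| 0.2 | 0.177, 0.352 | 0.125, 0.609 |
| 0.3 | 0.166, 0.394 | 0.117, 0.667 |
| 0.5 | 0.140, 0.516 | 0.099, 0.807 |
| 0.75 | 0.099, 0.807 | 0.070, 0.979 |

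The R² that brings the MDE down to 0.10 is 1 − (0.10/MDE)²: 1 − (0.10/0.198)² = 0.745 for the arm contrasts and 1 − (0.10/0.140)² = 0.49 for the main effects.

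**The case against.** **The scale is not defined.** The plan says "Minimum Detectable Effect (MDE) of 0.10 standard units" without saying that this is a difference in SDs. If 0.10 were Cohen's f for a two-arm comparison, then d = 2f = 0.20. That needs 394 per arm by noncentral t, or 4 × 394 = 1576 in total, and 400 v 400 gives power 0.806. A correlation of 0.10 behaves similarly: about 783 for a two-arm comparison, with power 0.81 at 800. On these scales 1600 is about right for the planned contrast, and the fault would be an unlabelled unit. This may be how the number arose, but nothing in the text says so. A competing guess is equally unstated: 1600 is close to the 1570 needed in each arm, so a per-arm size may have been used as the total. Either way, the detectable mean difference is 0.20 SD.

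**The main null is an omnibus one.** With 0.10 read as f in a 3-df F test, power is 0.93 at alpha 0.05 and 1096 respondents would suffice. That meets the 0.80 target but does not explain 1600. With alpha divided by six for the six primary items, power is 0.7996, but the plan states no such correction.

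**The inputs lie in an earlier experiment.** The plan does cite that experiment, adjusts for covariates and calls trust in doctors the most prognostic. A pooled, adjusted calculation cannot be excluded. It would need R² of about 0.49, or about 0.35 if one-sided as well. It would also power a contrast that question 5 does not specify, and could not apply to the unadjusted estimator.

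**The form waives justification.** It does, but it asks for precision, and the authors chose to state a figure.

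What stands is that the 29% depends on alpha, sidedness, allocation and R² that the plan leaves open, and that the cause of the discrepancy cannot be settled from the document.

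**Conclusion.** The concern holds. Read as a mean difference in SD units, the stated MDE is about half of what the registered contrast can detect with 0.80 power: 0.198 SD against 0.10 SD. Power at 0.10 SD is about 0.29, so a true effect of that size would be missed about seven times in ten. Because the 95% CI half-width is 0.139 SD, even an estimate of exactly zero would not exclude 0.10 SD.

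These figures assume equal arms, two-sided 5% and no covariate gain. The conclusion does not depend on them closely: the pooled main effects, a one-sided 5% test and R² up to 0.3 each leave the MDE above 0.10 SD. No allowance was made for multiplicity or for differences between the ten faces in each arm; the Bonferroni figure shows that a multiplicity correction would raise the MDE further. The error lies in the stated sensitivity. The randomisation and the estimator are not affected.

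**What to change.** Keep N = 1600 and replace the power statement, for example: *1600 observations (400 per arm) give 0.80 power at two-sided alpha 0.05 to detect 0.20 SD in each contrast with White Male, and 0.14 SD for the race and gender main effects, before covariate adjustment.* If the authors intended another alpha or sidedness, they should put in their own values and recompute.

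If a smaller MDE is to be claimed, define standard units and state the contrast, alpha and the R-squared from the earlier experiment that yield it. In reporting, a null result should not be described as ruling out 0.10 SD unless the confidence interval does so.

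The cost is wording, plus a less favourable stated sensitivity. No extra respondents are needed and the analysis does not change. Keeping 0.10 SD as a real target for the unadjusted contrasts would instead need about 6280 respondents, or 3140 for the main effects.

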# 8) Anything else you would like to pre-register? (e.g., secondary analyses, variables collected for exploratory purposes, unusual analyses planned?)

This is a replication of a study conducted on MTurk (AsPredicted #9068). As in previous study, all exclusion criteria are applied \*before\* the study begins so that excluded respondents are deemed ineligible to participate before any study data are collected.

### 1) Have any data been collected for this study already?

It's complicated. We have already collected some data but explain in Question 8 why readers may consider this a valid pre-registration nevertheless.

### 2) What's the main question being asked or hypothesis being tested in this study?

The main question is whether the race and gender of a simulated doctor causes participants in an analogue patient experiment to give lower satisfaction ratings and report less confidence in their diagnosis. The main (null) hypothesis being tested is that there are no differences in confidence or satisfaction ratings across four treatment arms that randomize the race and gender of a putative doctor.

### 3) Describe the key dependent variable(s) specifying how they will be measured.

• Primary outcome measures:

**AsPredicted** 

- 1) Confidence in doctor's diagnosis:
- We will combine the following visual analogue scales into an index (sum and divide by 2):
- How confident are you that this doctor made the correct diagnosis? [0-100]
- How confident are you that this doctor recommended the correct treatment plan? [0-100]
- Which diagnosis do you think is more likely to be correct? [the doctor's diagnosis (1); online symptom checker (2)]

• Would you ask the doctor to perform additional diagnostic tests? (Such as the CT scan recommended by the Symptom Checker). [yes (1); no (0)] 2) Satisfaction.

- What number would you use to rate your care during this emergency room visit? [0-100]
- Would you recommend this doctor to your friends and family? [5-point likert scale]
- Secondary outcome measures:
- 1) Warmth and Competence of Doctor (7-item warmth-competence scale)
- 2) Fairness of the cost of an ER visit.
- You would be charged about \$350 for this emergency department visit. How fair do you think this charge is? [0-100]

### 4) How many and which conditions will participants be assigned to?

This is a 2x2 experimental design. Subjects will be randomly assigned to one of four possible conditions: Black Female, Black Male, White Female, White Male. Within each condition, subjects are randomly assigned 1 of 10 possible putative doctors. We have a total of 40 putative doctors, 10 for each condition. For example, 10 Black Female doctors, etc. These are, in fact, actors selected from the Chicago Face Database. Given that the vast majority of Emergency Physicians in the United States are white men, the White Males condition serves as the "control".

### 5) Specify exactly which analyses you will conduct to examine the main question/hypothesis.

For all enumerated outcome variables, we will use a linear regression of the outcome on treatment assignment (with White Male as the omitted category), with robust standard errors. In addition to the basic "difference in means" estimator, we will also conduct regression analyses with covariate adjustment. In addition to standard demographic covariates, we also include a trust in doctor's measure, self-assessed health, insurance coverage status, recent emergency department visit experience, the gender and race of the respondent's primary care doctor (if applicable), and whether subjects have unpaid medical bills. Preliminary results indicated that trust in doctors is the most prognostic covariate for the outcomes. We also plan to conduct the following sub-group analyses to estimate conditional average treatment effects:

- 1) By sex (male or female).
- 2) Age (individuals born before 1965 versus those born in 1965 or after)

3) Race (black or white), but it's unlikely that we will successfully recruit many black respondents given the demographic characteristics of the MTurk subject pool.

4) Prejudice. We have a 4-item measure of racial prejudice (Stereotype Endorsement) and a 4-item measure of gender prejudice (Hostile Sexism). We also plan to conduct exploratory analyses of treatment effect heterogeneity using Bayesian Additive Regression Trees (BART).

